APPENDIX A. POST PRANDIAL LIPIDS AND DE NOVO LIPOGENESIS SUB-STUDIES

Purpose and Background

While fasting lipids reflect steady state and remnants from the previous day's diet, the patterns of lipids following a meal reflects important aspects of metabolic health (or dysfunction) especially in patients with NAFLD. Gemcabene is proposed to improve postprandial lipids in several ways. First, it is a dual inhibitor of both cholesterol synthesis and fatty acid synthesis. In addition, it decreases plasma levels of apoC-III, which then leads to increased clearance of VLDL particles, lowering circulating TG levels. The mechanism of apoC-III lowering is thought to be through inhibition of the expression of apoC-III.

12 SUB-STUDY SUMMARY

12.1 MEAL CHALLENGE SUB-STUDY & DEUTERATED WATER TRACER SUB-STUDY

| | |
|---------------------------|---|
| Title: | Meal Challenge Sub-Study |
| Study Description: | Provides measurement of postprandial lipids in 10 participants |
| Endpoints: | 
Primary Endpoint:
 
 Incremental area under the curve for TG concentration in plasma, chylomicrons and VLDL 
Secondary Endpoint:
 
 Incremental AUC for apoB and apoC-III in plasma, chylomicrons and VLDL |
| Title: | Deuterated Water Tracer Sub-Study |
| Study Description: | Provides measurement of postprandial lipids and will be performed simultaneously in the same 10 participants who are participating in the Meal Challenge Sub-Study |
| Endpoints: | 
Primary Endpoint:
 
 Change in fractional hepatic De Novo Lipogenesis (DNL) and fractional cholesterol synthesis (DNC) after twelve weeks of gemcabene 
Secondary Endpoint:
 
 Change in absolute hepatic De Novo Lipogenesis (DNL) and absolute cholesterol synthesis (DNC) after twelve weeks of gemcabene |
| Study Population: | The sample for this study will include n=10 participants with NAFLD (~50% boys and ~50% girls) who are participating in the GEM-IIT-601 study. The |

sub-study will only be conducted at Emory. All Emory site participants will be invited to participate in the sub-study until 10 have been enrolled .

| | |
|--|---|
| Description of Sites/Facilities Enrolling Participants: | Emory University |
| Description of Study Intervention: | No intervention; only blood collection will occur |
| Study Duration: | 12 months |
| Participant Duration: | 12 weeks |

13 STUDY POPULATION

The sample for this study will include n=10 participants with NAFLD (~50% boys and ~50% girls) who are participating in the GEM-IIT-601 study. The sub-study will only be conducted at Emory. All Emory site participants will be invited to participate in the sub-study until 10 have been enrolled.

13.1 INCLUSION CRITERIA * *ADDITIONAL INCLUSION AND EXCLUSION CRITERIA (IN ADDITION TO THE MAIN STUDY CRITERIA)*

In order to be eligible to participate in this study, an individual must meet all of the following criteria:

- 10. Willing to participate in the sub-study and complete all sub-study procedures at Baseline and Week 12 visits
- 11. History of hypertriglyceridemia

13.2 EXCLUSION CRITERIA * *ADDITIONAL INCLUSION AND EXCLUSION CRITERIA (IN ADDITION TO THE MAIN STUDY CRITERIA)*

An individual who meets any of the following criteria will be excluded from participation in this study:

- 22. Food allergies including gluten sensitivities
- 23. Known reaction to deuterated water

14 METHODS

After consent and assent to the main study, participants at Emory University will be informed of the sub-study at the Screening visit. Consent and assent for the sub-study will be obtained through providing details of the sub-study and procedures and through discussion. The postprandial lipid study will take place at the Baseline and Week 12 visit. Prior to the day of the visit, the participants will have a standardized meal provided for their evening meal. They will be asked not to consume any sugar

containing beverages including juice. The meal will be identical at Baseline and Week 12 and will consist of a commercially prepared frozen dinner that can be microwaved at the time of consumption. It will be shipped frozen to the participant's home along with instructions.

Deuterated water: De novo lipogenesis and cholesterol synthesis can be studied by measuring the incorporation of deuterium from deuterated water into VLDL-TG palmitate and plasma free cholesterol. Two 60 ml bottles of deuterated water (D, 70%) will be provided the evening prior to the DNL and DNC assessments. One bottle will be consumed with the standardized evening meal and one bottle 3 hours later around bedtime.

No food or flavored drinks will be allowed after 7 pm the day prior to the visit to ensure 8 hours of fasting. Participants will be asked to consume one glass of water in the morning prior to driving to the research center to ensure good hydration at the time of the sub-study.

On the morning of the visit, at the pediatric research unit, participants will have an IV placed during the initial blood draw to make repeated blood draws more comfortable. After fasting labs are completed, a standardized breakfast will be provided (approximately 30% fat [~12% polyunsaturated, 8% saturated, and 10% monounsaturated], 15% protein and 55% carbohydrates consumed in combination with a juice beverage). The standardized breakfast will be enriched with fructose to stimulate DNL and will be identical at Baseline (Week 0) and Week 12 assessments. It will be a fixed meal and not calorie-adjusted for body weight.

Blood samples will be drawn at 0, 2, 4, and 6 hours to assess the biological measures of interest. At each timepoint, 14 mL of blood will be collected in spray-dried K2 EDTA vacutainers and immediately placed on ice. Blood samples will be transported to the lab within 30 minutes, spun and the plasma aliquoted. At each blood collection timepoints, four (4) mL of plasma will be stored at 4°C and transported to the Biomarker Core Laboratory, Atlanta VAMC ([name] lab) on the same day for lipoprotein fractionation by density ultracentrifugation. Two (2) plasma aliquots from each timepoint will be stored at -80 °C.

| Timepoint (hours) | 0 | 2 | 4 | 6 | Total amount of blood per assessment |
|-----------------------------------|----------|----------|----------|----------|---|
| K2 EDTA | 14 ml | 14 ml | 14 ml | 14 ml | 56 ml |
| PK Sampling (Week 12 only) | 3 ml | 3 ml | 3 ml | 3 ml | 12 ml |

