1.2 SCHEMA

1.3 SCHEDULE OF ACTIVITIES (SOA)

Table 1. Schedule of Activities

| | Screening (-6 weeks) | Baseline (Day 1 +/- 2 days) | Week 2 (Day 15+/- 7 days) | Week 6 (Day 43+/- 10 days) | Week 12 (Day 85 +/- 10 days) | Week 16 Follow- up (phone call) Day 113 +/- 10 days | Early Termination Visit | Week 28 Long-Term Follow-up (Month 3) +/- 2 weeks | Week 36 Long-Term Follow-up (Month 6) +/- 2 weeks | Week 60 Long-Term Follow-up (Month 12) +/- 2 weeks |
|--|-------------------------|--------------------------------------|------------------------------------|--|---|---|-------------------------------|---|---|--|
| Informed Consent and HIPAA Authorization | X | | | | | | | | | |
| Review Inclusion/Exclusion Criteria | X | X | | | | | | | | |
| Demographics & Medical History | X | | | | | | | | | |
| Physical Exam | | X | | | X | | X | X | X | X |
| Vital Signs ^A | X | X | X | X | X | | X | X | X | X |
| Standardized lifestyle counseling | | X | | | | | | | | |
| Height, weight, (calculated BMI) waist and hip measurements ^C | X | X | X | X | X | | X | X | X | X |
| Alcohol Use Disorders Identification Test (AUDIT) | X | | | | | | | | | |
| Dietary Assessment (Food Frequency Questionnaire) | | X | | | X | | X | | | |
| MRI | | X | | | X | | X | X | X | X |
| ECG | | X | X | | | | | | | |
| PROMIS Questionnaires (fatigue, depression, anxiety) | | X | | | X | | X | | | |
| Beverage Questionnaire | | X | | | X | | X | | | |
| Tanner Staging (self-administered) | X | | | | | | | | | |
| Physical Activity Assessment (Block) | | X | | | X | | X | | | |
| Local Urine Pregnancy Test (WOCBP) | | X | X | X | X | | X | X | X | X |
| Urinalysis (UA) | X | X | X | X | X | | X | X | X | X |
| Blood Draw ^B | X | X | X | X | X | | X | X | X | X |

| | | | | | | | | | | |
|----------------------------------|---|---|---|---|---|---|---|---|---|---|
| De novo lipogenesis (substudy) | | X | | | X | | | | | |
| Postprandial lipid (substudy) | | X | | | X | | | | | |
| Instructions for Drug Compliance | | X | X | X | | | | | | |
| Drug Dispense | | X | | X | | | | | | |
| Identify clinical follow-up plan | | | | | X | | X | | | |
| Adverse Events Review | | X | X | X | X | X | X | X | X | X |
| Concomitant Medication Review | X | X | X | X | X | X | X | X | X | X |
| Assess Drug Accountability | | | X | X | X | | X | | | |

A – Vital signs to include: temperature, pulse, respirations, and seated blood pressure

B – See details below in Table 2. Blood Draw Schedule

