Procedures in this protocol are minimized and include 1) blood draws 2) MRI and 3) IV placement for repeated blood draws. To minimize risk to the participants, all blood draws and IV placements will be performed by pediatric experience staff in the research centers. All MRI's will be without contrast and without any sedation as these are the two primary risks of MRI.

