8.3 ADVERSE EVENTS AND SERIOUS ADVERSE EVENTS

8.3.1 DEFINITION OF ADVERSE EVENTS (AE)

Adverse event means any untoward medical occurrence associated with the use of an intervention in humans, whether or not considered intervention-related (21 CFR 312.32 (a)).

An adverse event is defined as any untoward medical occurrence in a clinical investigation subject administered a pharmaceutical product, which does not necessarily have a causal relationship with this treatment. An adverse event can therefore be any unfavorable and/or unintended sign (including an abnormal laboratory finding), symptom, or disease temporally associated with the use of an investigational medicinal product, whether or not related to the investigational medicinal product. All adverse events, including observed or volunteered problems, complaints, or symptoms, are to be recorded on the appropriate eCRF.

Adverse events, which include abnormal and clinically significant clinical laboratory test variables, will be monitored and documented from the time of first dose of study drug (Study Day 1) until study participation is complete (the Follow-up Visit). Subjects should be instructed to report any adverse event that they experience to the Investigator. Beginning with the signing of the informed consent until the time of the first dose of study drug (Study Day 1), Investigators should make updates to medical history and record any pre-existing medical condition or signs or symptoms that changes in severity, frequency,

or seriousness in the medical history. Serious adverse events that occur prior to the first dose of study drug (Study Day 1) should be reported as an update to medical history as well as be reported on the appropriate adverse event eCRF. Beginning with the first dose of study drug (Study Day 1), Investigators should make an assessment for adverse events at each visit and record all adverse events, non-serious and serious, on the appropriate adverse event eCRF.

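### The sub-study tracer is scheduled before the only pre-dose pregnancy test and the Baseline eligibility review, and the adverse-event rules it relies on conflict

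*Combined protocol and SAP*

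**What the plan says.** Appendix A, section 14 describes the tracer: "Two 60 ml bottles of deuterated water (D, 70%) will be provided the evening prior to the DNL and DNC assessments". It continues: "One bottle will be consumed with the standardized evening meal and one bottle 3 hours later around bedtime". On the standardized dinner that goes with the first bottle it says: "It will be shipped frozen to the participant's home along with instructions". The child then travels to the research unit the next morning, has an IV placed and eats a fructose-enriched breakfast. This is done at Baseline and again at Week 12.

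The sub-study summary in section 12.1 describes the intervention differently: "No intervention; only blood collection will occur". Section 13.2 excludes children with a "Known reaction to deuterated water". The procedure-risk paragraph of section 2.3.1 reads: "Procedures in this protocol are minimized and include 1) blood draws 2) MRI and 3) IV placement for repeated blood draws".

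In Table 1 (section 1.3) the pregnancy-test row begins "Local Urine Pregnancy Test (WOCBP) | | X | X | X | X": blank at Screening, first marked at Baseline. The inclusion/exclusion review is marked at both Screening and Baseline. The Baseline column has a window of ±2 days.

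Appendix A has no adverse-event rules of its own; section 15.1 refers to the main protocol. There, section 8.3.1 says that adverse events "will be monitored and documented from the time of first dose of study drug (Study Day 1) until study participation is complete", with earlier non-serious changes entered as medical history and earlier serious events entered in both places. Section 8.3.4 instead has coordinators record events that start at any time after consent. Section 8.3.3.2 grades relationship to the study intervention only, on a two-level scale.

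**The concern.** Three things do not fit together.

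First, if the schedule is followed as written, the first research substance a sub-study child takes comes ahead of two checks that the trial placed at Baseline: the only pregnancy test before dosing and the repeat eligibility review. A child found ineligible at that visit would already have taken the tracer.

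Second, the summary and the risk section do not describe what section 14 does, so someone reading only those parts would not know that a tracer and a test meal are given.

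Third, the safety data may treat the two tracer sessions differently. Safety is part of the primary objective, and the trial is single-arm and open-label, so no control group would show the background rate of reactions to the sub-study procedures. Nausea and dizziness are already listed as common gemcabene events in 2.3.1. A similar complaint after the tracer, meal or IV could be read as a drug effect at Week 12, yet might not enter the adverse-event data at Baseline.

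**Working it through.** The plan states no figure on this point. The check is one of sequence and wording, followed by simple counts.

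1. **Order of events at Baseline.** Section 14 puts both bottles on the evening before the assessment. Home use is inferred: the dinner is shipped to the home, the first bottle goes with that dinner, and the child travels in next morning. Table 1 puts the first pregnancy test and the second eligibility review at Baseline. With a one-day Baseline visit the order is tracer, then test and review. With a split visit inside ±2 days the checks could come first, but neither Table 1 nor Appendix A requires it.

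2. **What Screening covers.** A full inclusion/exclusion review is scheduled there, so known or suspected pregnancy and a known tracer reaction can be asked about. Exclusion 10 also names a positive pregnancy screen, and no test is scheduled at Screening to supply that result. Screening may be up to six weeks earlier.

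3. **When recording starts.** Section 14.1 places the Baseline session before gemcabene begins.

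| Non-serious reaction | Under 8.3.1 | Under 8.3.4 |
|---|---|---|
| Baseline session (before first dose) | Medical history | Recorded as an event |
| Week 12 session | Adverse event | Recorded as an event |

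The two sessions are treated differently under 8.3.1 and alike under 8.3.4. Serious events before first dose reach the adverse-event form under either section.

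4. **How causality is graded.** In 8.3.3.2, a related event needs a time course consistent with the drug **and** no other identifiable cause. An unrelated event needs a time course that rules the drug out **and** another suspected cause. Take a tracer, meal or IV reaction at Week 12 in a child taking gemcabene daily. If the time course is compatible with the drug, the unrelated definition fails. Another cause can be identified, so the related definition fails too. The event fits neither, and the same section tells the assessor always to suspect the study product. Section 9.4.4 tabulates relationship to study intervention only.

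5. **Size.**
   - Sub-study children: 10 of 40 enrolled, 10/40 = 25%; about half are girls, so about 5.
   - Tracer sessions: 10 × 2 = 20, of which 10 are before first dose.
   - Volume per session: 2 × 60 ml = 120 ml.
   - One affected child in a safety set of 40: 1/40 = 2.5 percentage points.

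6. **Reaction rate.** None is given. For illustration only, with an assumed rate p per child at one session, the chance of at least one reaction among 10 children is 1 − (1 − p)^10: 9.6% for p = 1%, 40.1% for 5% and 65.1% for 10%. If none of the 10 reacted, the one-sided 95% upper bound would be 1 − 0.05^(1/10) = 25.9%, so the sub-study could not settle the rate itself.

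**The case against.** There is a good deal to say for the plan. Eligibility is reviewed at Screening, including known or suspected pregnancy, and the Baseline window leaves room to test before the bottles are drunk. Section 8.3.4 records events from consent, and sub-study consent comes before the tracer, so Baseline reactions need not be lost. Section 8.3.3.2 tells the assessor to weigh other causes, and its category labels extend to possibly and unlikely related, so a sensible investigator would name the tracer. The unanticipated-problem definition in 8.4.1 also refers to research procedures. Section 9.4.4 counts each event once per participant, so a repeat adds nothing, and no planned analysis compares pre-dose with on-treatment events. The consent pages were removed from the public documents, so nothing can be inferred about what families were told.

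All of this limits the point. It does not settle it. The window permits the safer reading of the order without requiring it. The conflict between 8.3.1 and 8.3.4 remains whichever is followed. Judgement can bridge the causality definitions only by departing from their wording. The 8.4.1 route applies only to events that are unexpected, related or possibly related, and suggest greater risk than was known, not to ordinary complaints.

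A reader might go further and infer that the tracer endangers a pregnancy. The documents do not support that: the pregnancy warning in 2.3.1 concerns gemcabene and rests on rat studies, and the exclusion in 13.2 may be purely precautionary. A reader might also infer that tracer reactions will be missed at Baseline and charged to gemcabene at Week 12. That is not established either, for the reasons given from 8.3.4 and 8.3.3.2.

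**Conclusion.** The point holds in a limited form. As scheduled, the tracer precedes the only pre-dose pregnancy test and the second eligibility review, though not the Screening review. Section 12.1 contradicts section 14, and 2.3.1 is incomplete against it. The sub-study depends on adverse-event rules that disagree about when recording starts and on a causality scale that does not accommodate a reaction to a sub-study procedure. Unequal handling of the two sessions and misattribution at Week 12 are therefore possible, not certain.

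At most 10 children are affected, and each one who contributes a newly counted event moves incidence by 2.5 percentage points. No total effect can be given, because no reaction rate is stated. The conclusion assumes that the bottles are drunk at home, that the Baseline visit is not split, that the sub-study fills to 10, and that all 40 enrolled children are dosed. The order of checks and the event rules deserve a change before the sub-study runs; the 12.1 and 2.3.1 corrections alone would be clerical.

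**What to change.** - Reconcile section 14 with Table 1 on the order of the first tracer bottle, the pregnancy test and the Baseline eligibility review, and state that order in Appendix A. The sponsor must decide what it should be.
- Reconcile 8.3.1 and 8.3.4 on when adverse-event recording starts, so that both tracer sessions are handled in the same way, and refer to the result in section 15.1.
- Add one case report form field for relation to sub-study procedures (tracer, meal or IV), and show those events separately in the 9.4.4 tables.
- Correct the intervention line in 12.1 and the procedure list in 2.3.1 to match section 14.

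The cost is protocol wording, one form field, one table row and, if the order changes, a different sequence of existing checks for at most 10 children. The main efficacy analysis and the sample size are not touched.

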14.1 PART 2: DE NOVO LIPOGENESIS

Study Subjects: 10 adolescents (as described above)

Study Design: Hepatic de novo lipogenesis will be measured in the fasting state (0 HR) and during the fructose enriched meal challenge (0, 2, 4 and 6 HRS) before Gemcabene treatment begins (Week 0) and after treatment is complete (Week 12).

Sample Collection and Processing:

- (1) VLDL (Sf20-400) particles will be isolated from 1 mL of plasma at the Biomarker Core Laboratory, split in two equal VLDL aliquots (one primary and one back-up sample), frozen at -80 °C and shipped to Metabolic Solutions, Inc. for triglyceride isolation and deuterium enrichment of VLDL-TG palmitate by IRMS.
- (2) Plasma (250 µL) will be collected at 0, 2, 4 and 6 HRS and frozen at -20 °C for body water enrichment analyses (Metabolic Solutions, Inc.). Spray-dried K2 EDTA vacutainers will be used to collect plasma for body water enrichment analyses.
- (3) VLDL-TG palmitate concentration

Data Analysis: Deuterium enrichment in VLDL-TG palmitate and plasma water will be determined by IRMS. Fractional DNL will be calculated from body water and VLDL-TG-palmitate deuterium enrichment using precursor-product relationships. Absolute DNL will be calculated as Fractional DNL x VLDL-TG palmitate pool size.

Endpoints:

Primary Endpoint:

- Fractional hepatic DNL in the fasting state (0 HR) and during meal stimulation (2 HR, 4 HR, 6 HR)

Secondary Endpoint:

- Absolute hepatic DNL in the fasting state (0 HR) and during meal stimulation (2 HR, 4 HR, 6 HR)

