2.2 BACKGROUND

Introduction to Gemcabene: Gemphire Therapeutics Inc. (Gemphire) is developing gemcabene calcium (also denoted as CI-1027 or PD72953 and in this protocol referred to as gemcabene) for multiple indications including:

- 1.) As an adjunct to diet and statin therapy for the treatment of patients with dyslipidemia who require additional low-density lipoprotein cholesterol (LDL-C) lowering such as patients with homozygous familial hypercholesterolemia (HoFH) and heterozygous FH (HeFH) and atherosclerotic cardiovascular disease (ASCVD).
- 2.) To reduce triglycerides (TG) in patients with severe hypertriglyceridemia (TG \geq 500 mg/dL),
- 3.) To reduce or stop progression of hepatic steatosis in patients with nonalcoholic fatty liver disease (NAFLD)/nonalcoholic steatohepatitis (NASH).

To date 18 clinical studies evaluating gemcabene have been conducted (17 completed and 1 terminated for business reasons) evaluating a total of 1278 healthy adult volunteers and participants with 901 exposed to gemcabene providing extensive safety data and preliminary efficacy data for triglyceride reduction. No studies have previously been conducted in NAFLD populations.

Brief Mechanism of Action Summarized from Investigator Brochure Version 2: Gemcabene is the monocalcium salt of a dialkyl ether dicarboxylic acid and is a new class of lipid-regulating compounds because it has 2 terminal gem-dimethyl carboxylate moieties. It has several mechanisms of action including 1) enhancing the clearance of VLDL and 2) blocking the production of hepatic TG and cholesterol synthesis.

The enhanced clearance of VLDL is through decreased apolipoprotein C-III, an apolipoprotein that when elevated can mask apoE on VLDL remnants and inhibit LPL mediated TG lipolysis. Elevated apoC-III is associated with increased CVD risk. Gemcabene decreases apoC-III through decreased expression of mRNA, likely decreasing protein production. This leads to increased VLDL-remnant clearance and enhances LPL activity with the overall effect of lowering LDL-C and TG.

Gemcabene also has effects within the hepatocytes. In primary rat hepatocytes, gemcabene markedly blocked radiolabeled acetate incorporation into both TG and cholesterol. AcetylCoA carboxylase (ACC1) is the rate limiting step in de novo lipogenesis (DNL). Gemcabene may reduce ACC1 mRNA expression as well as inhibit ACC1 enzymatic activity, suggesting that it blocks the ACC1 step during DNL.

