monkeys, over 26 weeks at >30 mg/kg/day fatty changes were seen in the liver and kidneys. Carcinogenicity studies are ongoing in mice and rats. No mutagenic effects were seen in genetic toxicity studies. Developmental toxicity studies demonstrated abnormalities and teratogenicity at doses >10 mg/kg/day in rats but none in rabbits.

Summary of clinical studies with Gemcabene from the Investigator Brochure Version 2:

Phase 1 PK studies have demonstrated that oral gemcabene is rapidly absorbed with exposure increasing approximately linearly with dose. The primary route of elimination is renal. There is no clinically relevant effect on QT interval. There was a rapidly reversible increase in serum creatinine that is thought to be a hemodynamic change rather than a direct nephrotoxic effect because no change in protein to creatinine ration and no abnormal urine analysis was present. No effect was observed on blood pressure. There was an increase in the glucose disposal rate.

Phase 2 Efficacy studies have demonstrated benefits. In patients with dyslipidemia, monotherapy with 300 – 900 mg significantly lowered LDL-C compared to placebo in three Phase 2 studies. In patients with baseline TG \geq 200 mg/dL (Study 1027-04), gemcabene lowered TG by 39% at the 300 mg dose compared with 5% lowering by placebo.

Human safety data is drawn from this collection of 19 clinical studies. The most frequent reported adverse events in healthy volunteers for single doses were headache, asthenia, nausea, dizziness and somnolence. The most frequent adverse events for 4 weeks were headache, infection, nausea, asthenia, photosensitivity reaction, rhinitis, diarrhea, flatulence, dizziness and pharyngitis. In patients with dyslipidemia treated for 8 weeks, headache, asthenia, dizziness and pain were more frequent with gemcabene compared to placebo at doses from 300-900 mg. Nausea, dyspepsia and flatulence were more frequent with gemcabene compared to placebo. In 1272 healthy adult volunteers and patients, only 17 discontinued due to gemcabene related adverse events. There were no treatment related serious adverse events and no deaths.

Important Literature and Data Relevant to the Trial

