3 ENDPOINTS

Primary Endpoint:

- Percent change in ALT from Baseline to Week 12

Secondary Endpoints:

- Absolute change in ALT from Baseline to Weeks 6 and 12
- Percent change in ALT from Baseline to Week 6 and the mean of Week 6 and Week 12
- Absolute change and percent change in hepatic steatosis from Baseline to Week 12 as measured by MRI (volumetric fat fraction-hepafat)
- Absolute change and percent change in pancreatic fat from Baseline to Week 12 as measured by MRI (HepaFat)
- Absolute change and percent change in AST from Baseline to Week 6 and Week 12
- Absolute change and percent change in insulin sensitivity as assessed by fasting insulin, fasting glucose, and HOMA-IR from Baseline to Week 6 and Week 12
- Absolute change and percent change in GGT from Baseline to Week 6 and Week 12
- Absolute change and percent change in serum lipids including total cholesterol, non-HDL-C, HDL-C, VLDL-C, LDL-C, and triglycerides (TG) from Baseline to Week 6 and Week 12
- Absolute change and percent change in apolipoproteins including apoA-1, apoB, apoC-II, apoE and apoCIII
- Absolute change and percent change in inflammatory markers such as hsCRP, IL-1B, IL-6 and procollagen III.
- Absolute change and percent change in lipoprotein particle sizes (VLDL, HDL, LDL, chylomicrons [NMR])
- Absolute change and percent change in post-prandial lipids (total cholesterol, non-HDL-C, HDL-C, VLDL-C, LDL-C, TG, lipoprotein particle size)
- Absolute change and percent change in rate of de novo lipogenesis using stable isotope tracers
- Change in body composition measures by AMRA from Baseline to Week 12
- Absolute change and percent change in liver inflammation and fibrosis (LIF and cT1) scores by MRI (Liver MultiScan).
- Absolute change and percent change in anthropometric measures including height, weight, body mass index, and waist circumference from Baseline to Week 12

- Safety related endpoints including adverse events (AEs), vital signs, clinical labs, hematology and urinalysis
 - Treatment tolerance and compliance
-

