14.2 PART 3: CHOLESTEROL SYNTHESIS

Study Subjects: 10 adolescents (as described above)

Study Design: Cholesterol synthesis will be measured in the fasting state (0 HR) and during the meal challenge (6 HR) before Gemcabene treatment begins (Week 0) and after treatment is complete (Week 12).

Sample Collection and Processing:

- (1) Plasma (250µL) will be collected at 0, and 6 HRS and frozen at -20 °C for deuterium enrichment analyses of free cholesterol (Metabolic Solutions, Inc.) by IRMS.
- (2) Plasma free cholesterol concentration

Data Analysis:

Deuterium enrichment in plasma free cholesterol and plasma water will be determined by IRMS. The fraction of newly synthesized cholesterol (DNC) will be calculated from body water and cholesterol deuterium enrichment using precursor-product relationships. Absolute cholesterol synthesis will be calculated as DNL (%) x plasma (free) cholesterol concentration.

Endpoints:

Primary Endpoint:

- Fractional cholesterol synthesis in the fasting state (0 HR) and during meal stimulation (6 HR)

Secondary Endpoint:

- Absolute cholesterol synthesis in the fasting state (0 HR) and during meal stimulation (6 HR)

Measurements for DNL and DNC endpoints:

| Measurement | 0 HR | 2 HR | 4 HR | 6 HR |
|--|------------------|------|------|------|
| Deuterium enrichment in VLDL-TG palmitate (1 mL of plasma to isolate VLDL-TG for IRMS analyses) | X (in duplicate) | x | x | x |
| Deuterium enrichment in plasma water (0.25 mL of plasma for IRMS or Cavity Ringdown Spectrometer analyses) | x | x | x | x |
| Deuterium enrichment in plasma free cholesterol (0.25 mL of plasma for IRMS analyses) | x | | | x |
| VLDL-TG palmitate concentration (GCMS) | x | | | x |
| Plasma free cholesterol concentration (Enzymatic Method) | x | | | x |

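### Absolute hepatic DNL, as derived, is an amount in plasma VLDL that faster VLDL clearance can lower by itself, so a fall in it alone does not show reduced hepatic lipogenesis

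*Combined protocol and SAP*

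**What the plan says.** Section 14.1 defines two measures. The first is fractional: "Fractional DNL will be calculated from body water and VLDL-TG-palmitate deuterium enrichment using precursor-product relationships". The second is its product with a pool: "Absolute DNL will be calculated as Fractional DNL x VLDL-TG palmitate pool size". VLDL is isolated from plasma, and the only pool measure listed is a VLDL-TG palmitate concentration. No turnover, clearance or secretion rate is measured.

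Fractional DNL is the primary tracer endpoint. The product is secondary, listed in Section 12.1 as "Change in absolute hepatic De Novo Lipogenesis (DNL) and absolute cholesterol synthesis (DNC) after twelve weeks of gemcabene". Section 3 lists, among the trial's secondary endpoints, "Absolute change and percent change in rate of de novo lipogenesis using stable isotope tracers", without saying which of the two measures is meant.

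Section 2.2 credits gemcabene with two actions: faster VLDL clearance, and blocked hepatic production of triglyceride and cholesterol. On the first, acting through apoC-III, it says: "This leads to increased VLDL-remnant clearance and enhances LPL activity with the overall effect of lowering LDL-C and TG". The opening of Appendix A repeats the clearance mechanism. For size, Section 2.2 reports, in patients with baseline TG of at least 200 mg/dL, that "gemcabene lowered TG by 39% at the 300 mg dose compared with 5% lowering by placebo".

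Section 16.1 plans paired t-tests at 0.05. Neither it nor Section 14.1 limits how a fall in the product is to be read.

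**The concern.** A fraction times a plasma pool is an amount. It stands in for a synthesis rate only if the pool is cleared at the same rate at Baseline and Week 12, and the protocol expects treatment to change exactly that.

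The synopsis hypothesis includes down-regulation of DNL. Under its present label, a fall in the product could be read as support for that hypothesis when the liver makes as much palmitate as before and the plasma clears it faster. There is no control arm, and no turnover measure to tell the two apart.

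**Working it through.** The plan gives no sample size, power or expected value for absolute DNL, so there is no stated figure to reproduce.

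**Model.** One pool at steady state, with R = VLDL-TG palmitate secretion, R_D = its DNL-derived part, k = fractional clearance and t = labelling time:

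- pool: Q = R/k
- fraction: f(t) = (R_D/R)(1 − e^(−kt))
- planned product: f × Q = (R_D/k)(1 − e^(−kt))

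With R and R_D fixed, the product falls whenever k rises. At label plateau, an actual rate would be f × Q × k = R_D, which does not move with clearance.

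**Inputs.** From the documents: a 39% TG fall (Section 2.2), n = 10 (Section 13), a paired t-test at 0.05 (Section 16.1), and label taken with the evening meal and again 3 hours later (Section 14). Assumed, because the documents do not give them: clearance share of the TG fall 25% to 100% (log scale), VLDL-TG half-life 1 to 24 h, labelling time 8 to 14 h before the fasting sample, and SD of percent change 20% to 50%.

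**Label at plateau.** Clearance is multiplied by c = 0.61^(−share), and the product changes by 1/c − 1:

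| Share due to clearance | c | Change in product |
|---|---|---|
| 25% | 1.132 | −11.6% |
| 50% | 1.280 | −21.9% |
| 75% | 1.449 | −31.0% |
| 100% | 1.639 | −39.0% |

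With 34% (39 minus 5 points for placebo) in place of 39%, the range is −9.9% to −34.0%.

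**Label not at plateau, all of the 39% due to clearance, 8 to 14 h labelling:**

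| Half-life | Change in product | Change in fraction |
|---|---|---|
| 1 h | about −39% | 0 to +0.4% |
| 2 h | −36% to −39% | +1% to +6% |
| 4 h | −27% to −34% | +8% to +20% |
| 6 h | −21% to −29% | +16% to +29% |
| 12 h | −12% to −19% | +32% to +44% |
| 24 h | −7% to −11% | +46% to +53% |

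With half of the fall due to clearance, the 24 h row shrinks to −3% to −5%. The sign is negative throughout, although hepatic synthesis is unchanged by construction.

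**Chance of p < 0.05 from clearance alone** (n = 10, one-sample t-test on percent change, SD 20 / 30 / 40 / 50%): 1.00 / 0.95 / 0.78 / 0.59 for a 39% fall, and 0.87 / 0.54 / 0.34 / 0.24 for a 22% fall.

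**Can the fraction settle the cause?** At plateau, compare two cases. If clearance rises by 1/0.7, f is unchanged, Q falls 30%, the product falls 30%, and synthesis is unchanged. If R and R_D both fall 30%, f is unchanged, Q falls 30%, the product falls 30%, and synthesis has truly fallen 30%. The data are identical.

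**Cholesterol (Section 14.2).** The same kind of product is formed, using "Plasma free cholesterol concentration". Applying the same formula to a 39% clearance-driven pool fall, purely as an illustration, with an assumed 72 h half-life: at t = 8 h the fraction ratio is 0.1186/0.0741 = 1.60 and the product ratio is 1.60 × 0.61 = 0.976; at t = 14 h these are 1.57 and 0.959. The product moves only 2% to 4%, while the fraction rises 57% to 60%.

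**The case against.** The best defence is that the plan already ranks the measures sensibly. Fractional DNL is primary, the product is secondary, Section 9.4.9 places the sub-study under exploratory analyses, and the palmitate concentration is measured, so it can be shown beside the product. No text says that a fall in the product alone will be reported as reduced lipogenesis. All of this stands and limits the weight of the point. It does not remove the label, which claims a hepatic quantity that the formula does not deliver.

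A reader might also infer more than the documents support:

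- *That the product falls by the full 39% and false significance is near certain.* That is the ceiling. It gives all of the TG fall to clearance, although Section 2.2 also credits reduced production. The figure is for total TG, not VLDL-TG palmitate in adolescents, and Section 13.1 asks only for a history of hypertriglyceridemia, with no threshold.
- *That fractional DNL alone can arbitrate.* Before plateau, clearance alone raises it; at plateau, a proportional fall in secretion leaves it flat.
- *That the cholesterol product has the same bias.* Section 2.2 does not say that clearance of plasma free cholesterol rises, and with slow turnover the product is nearly unbiased.
- *That the sub-study exists to separate synthesis from clearance.* Appendix A presents the two together as ways in which postprandial lipids may improve.

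**Conclusion.** The point holds for absolute DNL as a matter of labelling and inference. The product measures newly made palmitate in plasma VLDL, and the clearance effect that the protocol expects pushes it downwards with no change in hepatic synthesis.

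The direction follows from the formula under a one-pool steady-state model, which the samples at 2, 4 and 6 hours after the meal will not meet exactly. The size rests on a clearance share and a half-life that the documents do not give, so the tabulated falls are a range of possibilities and not a prediction.

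The trial's primary endpoint and sample size, and the sub-study's primary endpoint, are not affected through this route in the way the product is: clearance does not lower fractional DNL in this model. The change is worth considering and is not a condition for the trial's main conclusions.

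**What to change.** - **Sections 12.1 and 14.1:** relabel the product as *concentration of newly synthesised palmitate in VLDL-TG*. Report it together with fractional DNL and the measured VLDL-TG palmitate concentration. The measurement table schedules that concentration only at 0 and 6 hours, so also say how the 2-hour and 4-hour values will be obtained.
- **Interpretation:** state that a fall in the product alone will not be reported as reduced hepatic lipogenesis, because without a turnover measure it cannot separate clearance from secretion. Do not pre-specify that a fall with an unchanged fraction is due to clearance.
- **Section 3:** say which measure the rate of de novo lipogenesis refers to.
- **Section 14.2:** report the cholesterol fraction, concentration and product together, with the turnover assumption stated.

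The relabelling, joint reporting and interpretation statements need wording only, with no new samples or assays. The small downside is that one secondary endpoint of an exploratory sub-study in 10 participants supports a weaker claim.
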